3.5 Informed Consent/Accent

The investigational nature and objectives of the trial, the procedures and treatments involved and their attendant risks and discomforts, and potential alternative therapies will be carefully explained to the patient or the patient's parents or guardian if the patient is a child, and a signed informed consent and assent will be obtained according to institutional guidelines.

3.6 Screening Procedures

Diagnostic or laboratory studies performed exclusively to determine eligibility for this trial must only be done after obtaining written informed consent. This can be accomplished through one of the following mechanisms: a) the COG screening protocol, b) an IRB-approved institutional screening protocol or c) the study-specific protocol. Documentation of the informed consent for screening will be maintained in the patient's research chart. Studies or procedures that were performed for clinical indications (not exclusively to determine eligibility) may be used for baseline values even if the studies were done before informed consent was obtained.

3.7 Eligibility Checklist

Before the patient can be enrolled, the responsible institutional investigator must sign and date the completed eligibility checklist. A signed copy of the checklist will be uploaded into RAVE immediately following enrollment.

3.8 Institutional Pathology Report

Immediately following enrollment, the institutional pathology report for the diagnosis under which the patient is being enrolled must be uploaded into RAVE. The report must include the associated study number and COG patient registration and accession numbers. Personal identifiers, including the patient's name and initials must be removed from the institutional pathology report prior to submission.

3.9 Study Enrollment

Patients may be enrolled on the study once all eligibility requirements for the study have been met. Patients who give informed consent for the protocol in order to undergo screening for eligibility are not considered enrolled and should not be enrolled until the screening is completed and they are determined to meet all eligibility criteria. Study enrollment is accomplished by CTSU OPEN (Oncology Patient Enrollment Network) <https://open.ctsu.org/open/>. For questions, please contact the CTSU OPEN helpdesk at <https://www.ctsu.org/CTSUCOntract.aspx>. Patients must be enrolled before treatment begins. The date protocol therapy is projected to start must be no later than five (5) calendar days after the date of study enrollment. **Patients must not receive any protocol therapy prior to enrollment.**

3.10 Dose Assignment

The dose level will be assigned via OPEN at the time of study enrollment.

4.0 PATIENT ELIGIBILITY

All clinical and laboratory studies to determine eligibility must be performed within 7 days prior to enrollment unless otherwise indicated. Laboratory values used to assess eligibility must be no older than seven (7) days at the start of therapy. Laboratory tests need **not** be repeated if therapy starts **within** seven (7) days of obtaining labs to assess eligibility. If a post-enrollment lab value is outside the limits of eligibility, or laboratory values are older than 7 days, then the following laboratory evaluations must be re-checked within 48 hours prior to initiating therapy: CBC with differential, bilirubin, ALT (SGPT) and serum creatinine. If the recheck is outside the limits of eligibility, the patient may not receive protocol therapy and will be considered off protocol therapy. Imaging studies must be obtained within 14 days prior to start of protocol therapy (repeat the tumor imaging if necessary).

Clarification in timing when counting days: As an example, please note that if the patient's last day of prior therapy is September 1st, and the protocol requires waiting at least 7 days for that type of prior therapy, then that patient cannot be enrolled until September 8th.

Important note: The eligibility criteria listed below are interpreted literally and cannot be waived (per COG policy posted 5/11/01). All clinical and laboratory data required for determining eligibility of a patient enrolled on this trial must be available in the patient's medical or research record which will serve as the source document for verification at the time of audit.

4.1 Inclusion Criteria

4.1.1 Age: Patients must be ≥ 2 and ≤ 18 years of age at the time of study enrollment.

4.1.2 Body Surface Area (BSA): Patients must have a body surface area $\geq 0.44 \text{ m}^2$ when enrolling on dose level -1. Patients must have a body surface area $\geq 0.35 \text{ m}^2$ when enrolling on dose levels 1, 2, or 3.

4.1.3 Diagnosis:

Part A: Patients with relapsed or refractory solid tumors (excluding medullary thyroid cancer) including CNS tumors and malignant melanoma are eligible. Patients must have had histologic verification of malignancy at original diagnosis or relapse except in patients with intrinsic brain stem tumors, optic pathway gliomas, or patients with pineal tumors and elevations of CSF or serum tumor markers including alpha-fetoprotein or beta-HCG.

Part B: Patients with medullary thyroid cancer (MTC), with or without bone marrow involvement, will be eligible for Part B. These patients will be enrolled at Dose Level 2, the recommended Phase 2 Dose determined in the dose escalation part of the study.

4.1.4 **Disease Status:**
Patients must have either measurable or evaluable disease (see Sections [12.2](#) and [12.3](#) for definitions).

4.1.5 **Therapeutic Options:** Patient's current disease state must be one for which there is no known curative therapy or therapy proven to prolong survival with an acceptable quality of life.

4.1.6 **Performance Level:** Karnofsky $\geq 50\%$ for patients > 16 years of age and Lansky ≥ 50 for patients ≤ 16 years of age (See [Appendix I](#)). Note: Neurologic deficits in patients with CNS tumors must have been relatively stable for at least 7 days prior to study enrollment. Patients who are unable to walk because of paralysis, but who are up in a wheelchair, will be considered ambulatory for the purpose of assessing the performance score.

4.1.7 **Prior Therapy**

4.1.7.1 Patients must have fully recovered from the acute toxic effects of all prior anti-cancer chemotherapy.

- a. **Myelosuppressive chemotherapy:**
At least 21 days after the last dose of myelosuppressive chemotherapy (42 days if prior nitrosourea).
- b. **Hematopoietic growth factors:** At least 14 days after the last dose of a long-acting growth factor (e.g. Neulasta) or 7 days for short-acting growth factor. For agents that have known adverse events occurring beyond 7 days after administration, this period must be extended beyond the time during which adverse events are known to occur. The duration of this interval must be discussed with the study chair.
- c. **Biologic (anti-neoplastic agent):** At least 7 days after the last dose of a biologic agent. For agents that have known adverse events occurring beyond 7 days after administration, this period must be extended beyond the time during which adverse events are known to occur. The duration of this interval must be discussed with the study chair.
- d. **Immunotherapy:** At least 42 days after the completion of any type of immunotherapy, e.g. tumor vaccines.
- e. **Monoclonal antibodies:** At least 3 half-lives of the antibody after the last dose of a monoclonal antibody. (See table on DVL homepage listing monoclonal antibody half-lives.)
- f. **XRT:** At least 14 days after local palliative XRT (small port); At least 150 days must have elapsed if prior TBI, craniospinal XRT or if $\geq 50\%$ radiation of pelvis; At least 42 days must have elapsed if other substantial BM radiation.
- g. **Stem Cell Infusion without TBI:** No evidence of active graft vs. host disease and at least 56 days must have elapsed after transplant or stem cell infusion.

4.1.8 Organ Function Requirements4.1.8.1 Adequate Bone Marrow Function Defined as:

- a. For patients with solid tumors without known bone marrow involvement:
 - Peripheral absolute neutrophil count (ANC) $\geq 1000/\text{mm}^3$
 - Platelet count $\geq 100,000/\text{mm}^3$ (transfusion independent, defined as not receiving platelet transfusions for at least 7 days prior to enrollment)
- b. Patients with known bone marrow metastatic disease will be eligible for study provided they meet the blood counts in [4.1.8.1.a](#) (may receive transfusions provided they are not known to be refractory to red cell or platelet transfusions). These patients will not be evaluable for hematologic toxicity. At least 5 of every cohort of 6 patients with a solid tumor must be evaluable for hematologic toxicity in the dose-escalation part of the study. If dose-limiting hematologic toxicity is observed, all subsequent patients enrolled must be evaluable for hematologic toxicity.

4.1.8.2 Adequate Renal Function Defined as:

- Creatinine clearance or radioisotope GFR $\geq 70\text{ml/min}/1.73\text{ m}^2$ or
- A serum creatinine based on age/gender as follows:

Age	Maximum Serum Creatinine (mg/dL)	
	Male	Female
2 to < 6 years	0.8	0.8
6 to < 10 years	1	1
10 to < 13 years	1.2	1.2
13 to < 16 years	1.5	1.4
≥ 16 years	1.7	1.4

The threshold creatinine values in this Table were derived from the Schwartz formula for estimating GFR (Schwartz et al. J. Peds, 106:522, 1985) utilizing child length and stature data published by the CDC.

- Urine protein: $\leq 30\text{ mg/dl}$ in urinalysis or $\leq 1+$ on dipstick, unless quantitative protein is $< 1000\text{ mg}$ in a 24 h urine sample.

4.1.8.3 Adequate Liver Function Defined as:

- Bilirubin (sum of conjugated + unconjugated) $\leq 1.5 \times$ upper limit of normal (ULN) for age
- SGPT (ALT) $\leq 110\text{ U/L}$. For the purpose of this study, the ULN for SGPT is 45 U/L.
- Serum albumin $\geq 2.8\text{ g/dL}$.

4.1.8.4 Adequate coagulation status Defined As:

- PT and INR $\leq 1.5 \times$ ULN

4.1.8.5 Adequate Pancreatic Function Defined As:

- Serum amylase $\leq 1.5 \times$ ULN and
- Serum lipase $\leq 1.5 \times$ ULN

THIS PROTOCOL IS FOR RESEARCH PURPOSES ONLY, SEE PAGE 1 FOR USAGE POLICY

4.1.8.6 Adequate Blood Pressure Control defined as:

A blood pressure (BP) \leq the 95th percentile for age, height, and gender ([Appendix VIII](#)) measured as described in [Section 6.4](#), and not receiving medication for treatment of hypertension. Please note that 3 serial blood pressures should be obtained and averaged to determine baseline BP (See [Section 6.4](#)).

4.1.8.7 Central Nervous System Function Defined as:

Patients with seizure disorder may be enrolled if receiving non-enzyme inducing anticonvulsants and well controlled. See [Appendix XIII](#) for a list of recommended non-enzyme inducing anticonvulsants.

4.1.8.8 Adequate Cardiac Function Defined As:

- No history of congenital prolonged QTc syndrome, NYHA Class III or IV congestive heart failure (CHF)
- No clinically significant cardiac arrhythmias, stroke or myocardial infarction within 6 months prior to enrollment
- QTc \leq 480 msec. Note: Patients with Grade 1 prolonged QTc (450-480 msec) at the time of study enrollment should have correctable causes of prolonged QTc addressed if possible (i.e. electrolytes, medications). See [Appendix XV](#) for a list of drugs that prolong QTc.

4.1.9 Informed Consent: All patients and/or their parents or legally authorized representatives must sign a written informed consent. Assent, when appropriate, will be obtained according to institutional guidelines.

4.1.10 Archival tumor tissue slides from either initial diagnosis or relapse must be sent per [Section 8.5.1.2](#) and [Appendix XI](#). If tumor tissue is unavailable, the study chair must be notified prior to enrollment.

4.2 Exclusion Criteria**4.2.1 Pregnancy or Breast-Feeding**

Pregnant or breast-feeding women will not be entered on this study due to risks of fetal and teratogenic adverse events as seen in animal/human studies. Pregnancy tests must be obtained in girls who are post-menarchal. Males or females of reproductive potential may not participate unless they have agreed to use two methods of birth control- a medically accepted barrier method of contraceptive method (e.g., male or female condom) and a second effective method of birth control- during protocol therapy and for at least 4 months after the last dose of XL184. Abstinence is an acceptable method of birth control.

4.2.2 Concomitant Medications

4.2.2.1 Corticosteroids: Patients receiving corticosteroids who have not been on a stable or decreasing dose of corticosteroid for at least 7 days prior to enrollment are not eligible.

4.2.2.2 Investigational Drugs: Patients who are currently receiving another investigational drug are not eligible.

4.2.2.3 Anti-cancer Agents: Patients who are currently receiving other anti-cancer agents are not eligible

4.2.2.4 Anti-GVHD agents post-transplant:

Patients who are receiving cyclosporine, tacrolimus or other agents to prevent graft-versus-host disease post bone marrow transplant are not eligible for this trial.

4.2.2.5 CYP3A4 active agents: Patients must not be receiving any of the following potent CYP3A4 inducers or inhibitors: erythromycin, clarithromycin, ketoconazole, azithromycin, itraconazole, grapefruit juice or St. John's wort. A list of other known CYP3A4 inducers and inhibitors that should be discontinued prior to initiation of protocol therapy and should be avoided during study therapy if reasonable alternatives exist is included in [Appendix IX](#).

4.2.2.6 Patients who are receiving systemic treatment anticoagulation are not eligible. Patients receiving prophylactic systemic anticoagulation will be allowed as long as eligibility PT/INR requirements are met (See [Section 4.1.8.4](#)).

4.2.2.7 Enzyme-inducing Anticonvulsants: Patients must not have received enzyme-inducing anticonvulsants within 14 days prior to enrollment (See [Appendix XIII](#) for a list of unacceptable enzyme inducing anticonvulsants).

4.2.2.8 QTc Agents: Patients who are receiving drugs that prolong QTc are not eligible (See [Appendix XV](#) for a list of agents).

4.2.3 Patients must be able to swallow intact tablets. Patients who cannot swallow intact tablets are not eligible.

4.2.4 Patients with active bleeding are not eligible. Specifically, no clinically significant GI bleeding, GI perforation, intra-abdominal abscess or fistula for 6 months prior to enrollment, no hemoptysis or other signs of pulmonary hemorrhage for 3 months prior to enrollment.

4.2.5 Patients with evidence of an acute intracranial or intratumoral hemorrhage on CT or MRI are not eligible (patients with evidence of resolving hemorrhage will be eligible).

4.2.6 Surgery: Patients who have had or are planning to have the following invasive procedures are not eligible:

- Major surgical procedure, laparoscopic procedure, open biopsy or significant traumatic injury within 28 days prior to enrollment.
- Central line placement or subcutaneous port placement is not considered major surgery but must be placed at least 3 days prior to enrollment for external lines (e.g. Hickman or Broviac) and at least 7 days prior to enrollment for subcutaneous port.
- Core biopsy within 7 days prior to enrollment.
- Fine needle aspirate within 7 days prior to enrollment.

THIS PROTOCOL IS FOR RESEARCH PURPOSES ONLY, SEE PAGE 1 FOR USAGE POLICY

- Surgical or other wounds must be adequately healed prior to enrollment

4.2.7 Patients on antihypertensive therapy for control of blood pressure at the time of enrollment are not eligible.

4.2.8 Patients with any medical or surgical conditions that would interfere with gastrointestinal absorption of this oral agent are not eligible.

4.2.9 Infection: Patients who have an uncontrolled infection are not eligible.

4.2.10 Patients who have received a prior solid organ transplantation are not eligible.

4.2.11 Patients who in the opinion of the investigator may not be able to comply with the safety monitoring requirements of the study are not eligible.

5.0 TREATMENT PROGRAM

5.1 Overview of Treatment Plan

Treatment Schedule Table	
Time	Agent
Days 1-28	Oral XL184*

*Refer to dosing nomogram in [Appendix II](#) for dosing schedule.

XL184 will be administered orally at approximately the same time as prescribed. XL184 should be taken on an empty stomach; patients should fast 2 hours before and 1 hour after taking the drug. Tablets should not be crushed or chewed; tablets should be swallowed whole. See also [Section 9.1.6](#) for medications and foods to be avoided.

A cycle of therapy is considered to be 28 days.

Drug doses should be adjusted based on the BSA calculated from height and actual body weight measured within 7 days prior to the beginning of each cycle, and according to the dosing nomogram (see [Appendix II](#)). Sites will fill out the number of prescribed tablets per day in the patient diary (see [Appendix III](#)). Patients must complete the patient diary with the date, time and number of XL184 tablets taken each day. The patient diary should be reviewed after completion of each treatment cycle.

If a patient vomits after the dose of XL184 is administered, the dose should not be repeated.

If a dose of XL184 is missed and less than 6 hours have passed since the scheduled dosing time, the dose should be taken immediately. If more than 6 hours have passed since the scheduled dosing time, the patient should not take the missed dose but should wait and take the next regularly scheduled dose.

5.2 Criteria for Starting Subsequent Cycles

A cycle may be repeated every 28 days if the patient has at least stable disease, has again met laboratory parameters as defined in the eligibility sections [4.1.8.1- 4.1.8.3](#) and [4.1.8.5](#), and has not experienced study-drug related adverse events warranting permanent discontinuation.

Patients who have a delay in starting subsequent cycles for resolution of toxicity should also have the required observations in [Section 8.1](#) until the start of the next cycle.

5.3 Dose Escalation Schema

5.3.1 *Inter-Patient Escalation- (Part A) COMPLETE*

The starting dose will be 30 mg/m² (Dose Level 1) with dose levels for subsequent groups of patients as follows.

Dose Level	XL184 Dose (mg/m² po daily)
-1	23
1*	30
2	40
3	55

** Starting Dose Level*

There will be no escalations beyond dose level 3 (55 mg/m²).

If the MTD has been exceeded at the first dose level, then the subsequent cohort of patients will be treated at a dose of 23 mg/m² (Dose Level -1).

With Amendment #5A, patients enrolled onto Part A of the study will be treated at the recommended Phase 2 dose, which has been determined to be Dose Level 2 (40 mg/m²).

5.3.2 *Part B: Patients with medullary thyroid cancer (MTC) can be accrued to a separate stratum if there are no available slots on Part A. These patients will be enrolled at one dose level below the dose level at which patients on Part A are actively enrolling, or at the starting dose level (Dose Level 1) if dose escalation has not yet occurred. COMPLETE*

With Amendment #5A, patients enrolled onto Part B of the study will be treated at the recommended Phase 2 dose, which has been determined to be Dose Level 2 (40 mg/m²).

5.3.3 *Intra-Patient Escalation (Patients with MTC only)*

Intra-patient dose escalation will be allowed for patients with MTC remaining on study in cycles of therapy subsequent to Cycle 1, once an MTD or recommended Phase 2 dose is identified, if the patient has not experienced dose-limiting toxicity at the dose at which they began therapy. Patients who are one dose level below the MTD can escalate to the MTD. Patients who are more than one dose level below the MTD can escalate one dose level per cycle until they reach the MTD as long as they do not experience a DLT when escalating. Sites have to confirm with the Study Chair and the COG Phase 1 Operations office that their patient may proceed with an intra-patient dose escalation following the completion of Cycle 1 or subsequent cycles. COMPLETE

5.4 Grading of Adverse Events

Adverse events (toxicities) will be graded according to the NCI Common Terminology Criteria for Adverse Events (CTCAE) version 4.0. All appropriate treatment areas should have access to a copy of the CTCAE version 4.0. A copy of the CTCAE version 4.0 can be downloaded from the CTEP website (<http://ctep.cancer.gov>). Any suspected or confirmed dose-limiting toxicity should be reported immediately (within 24 hours) to the

Study Chair.

5.5 **Definition of Dose-Limiting Toxicity (DLT)**

DLT will be defined as any of the following events that are possibly, probably or definitely attributable to XL184. The DLT observation period for the purposes of dose-escalation will be the first cycle of therapy. Any drug-related toxicity that requires a dose reduction in Cycle 1 will also be considered a DLT.

Dose limiting hematological and non-hematological toxicities are defined differently.

5.5.1 Non-Hematological Dose-Limiting Toxicity

5.5.1.1 Any Grade 3 or Grade 4 non-hematological toxicity attributable to the investigational drug with the specific exclusion of:

- Grade 3 nausea and vomiting of < 3 days duration
- Grade 3 diarrhea \leq 3 days duration
- Grade 3 liver enzyme elevation, including ALT/AST/GGT/bilirubin, that return to levels that meet initial eligibility criteria or baseline within 7 days of study drug interruption and that does not recur upon re-challenge with XL184. Note: For the purposes of this study the ULN for ALT is defined as 45 U/L. See [section 6.6](#) for dose modifications for liver toxicity.
- Grade 3 or 4 fever < 5 days duration.
- Grade 3 infection < 5 days duration.
- Grade 3 hypophosphatemia, hypokalemia, hypocalcemia or hypomagnesemia responsive to supplementation
- Grade 3 asymptomatic amylase or lipase elevation that resolves to \leq Grade 1 within 7 days of study drug interruption and that does not recur upon re-challenge with XL184. See [section 6.7](#) for dose modifications for pancreatic toxicity.
- Grade 3 proteinuria (urine protein/creatinine (P/C) ratio $>$ 1.9) unless it is confirmed with a second measurement within 72 hours.

5.5.1.2 Dose-limiting hypertension

- Any Grade 4 hypertension
- A blood pressure $>$ 25 mmHg above the 95th percentile for age, height, and gender ([Appendix VIII](#)) confirmed by repeated measurement is dose limiting.
- In patients who begin antihypertensive therapy a blood pressure $>$ 10 mmHg but \leq 25 mmHg above the 95th percentile for age, height, and gender ([Appendix VIII](#)) for $>$ 14 days is dose limiting.

5.5.1.3 QTc prolongation $>$ 500 ms that persists despite correction of serum electrolyte abnormalities will be considered dose limiting.

5.5.1.4 Any Grade 2 non-hematological toxicity that persists for \geq 7 days and is considered sufficiently medically significant or sufficiently intolerable by patients that it requires treatment interruption.

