5.5.1.5 Any toxicity requiring interruption of study drug during a cycle of therapy

THIS PROTOCOL IS FOR RESEARCH PURPOSES ONLY, SEE PAGE 1 FOR USAGE POLICY
for ≥ 7 days or which recurs upon drug challenge.

5.5.1.6 Note: Allergic reactions that necessitate discontinuation of study drug will not be considered a dose-limiting toxicity.

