6.4 Dose Modifications for Hypertension

- **Baseline blood pressure (BP)** is defined as the blood pressure obtained at the examination used for study enrollment. This baseline BP should be obtained as follows: 1) Obtain 3 serial blood pressures from the same extremity with the patient in the same position at rest with an appropriately sized cuff that are separated by at least 5 minutes. Avoid using the lower extremity if possible. 2) Average the systolic blood pressure from the 2nd and 3rd measurements. 3) Average the diastolic blood pressure from the 2nd and 3rd measurements. 4) The baseline BP is the average of the systolic over the average of the diastolic measurements.
- **Elevation** in either the systolic or diastolic blood pressure should be considered when following the algorithm below.
- **The upper limit of normal (ULN)** is defined as a BP equal to the 95th percentile for age, height, and gender. See [Appendix VIII](#).
- The NCI CTCAE will be utilized to determine the grade of hypertension for reporting purposes.
- Elevated BP measurements should be repeated on the same day to confirm the elevation. If confirmed, patients with elevated BP should have BP measurements performed at least twice weekly until BP is \leq ULN.
- The algorithm below will be used to manage XL184- related hypertension.
- Hypertension should be managed with appropriate anti-hypertensive agent(s) as clinically indicated. It is strongly recommended that nephrology or cardiology be consulted in the evaluation and management of hypertension.

Elevations in BP are based on systolic or diastolic pressures.

[†] Elevated blood pressure (BP) measurements should be repeated on the same day to confirm the elevation. Patients with elevated BP at any time should have BP measurements performed at least twice weekly until BP is within the ULN.

[§] ULN (Upper Limit of Normal) is a BP equal to the 95th percentile from age, height, and gender-appropriate normal values (Appendix VIII).

^{*} If BP >25 mm Hg above ULN for age (verified) or Grade 4 HTN at any time, hold drug. Study drug should also be held for BP ≤ 25 mm Hg above the ULN age for > 14 days or 35 mmHg above baseline for > 14 days. Antihypertensive agents can be used to control hypertension as clinically indicated after study drug is held.

[^] Anti-hypertensive therapy should be prescribed as clinically indicated, including the use of multiple anti-hypertensive agents.

[#] Baseline BP is defined in Section 6.4.

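### The rules for persistent treated hypertension, Grade 4 hypertension and proteinuria give conflicting instructions across 5.2, 5.5.1.2, 6.2.1, 6.3 and 6.4

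*Combined protocol and SAP*

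**What the plan says.** **Treated hypertension.** The DLT rule in 5.5.1.2 starts "In patients who begin antihypertensive therapy a blood pressure" and names the range above 10 and up to 25 mmHg over the 95th percentile, lasting more than 14 days. In 6.4, Arm 2 takes a patient no more than 10 mmHg above the upper limit of normal (ULN, the 95th percentile) who is still elevated on recheck, starts treatment and passes the patient to Arm 3. Arm 3 holds the drug if pressure stays elevated by up to 25 mmHg, or is more than 35 mmHg above baseline, beyond 14 days of treatment. It restarts only at a reduced dose. Footnote * of the algorithm repeats both conditions in the sentence beginning "Study drug should also be held for BP".

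**Other DLT clauses.** The list in 5.5 is disjunctive: "DLT will be defined as any of the following events". Section 5.5 adds: "Any drug-related toxicity that requires a dose reduction in Cycle 1 will also be considered a DLT". Section 5.5.1.1 covers Grade 3 or 4 "non-hematological toxicity attributable to the investigational drug with the specific exclusion of" a list in which hypertension does not appear. Section 5.5.1.4 covers a Grade 2 event that lasts at least 7 days "and is considered sufficiently medically significant or sufficiently intolerable by patients that it requires treatment interruption". Section 5.5.1.5 covers "Any toxicity requiring interruption of study drug during a cycle of therapy" when the interruption is 7 days or longer, or the toxicity recurs.

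**Grade 4 hypertension.** Section 5.5.1.2 makes it a DLT. Footnote * says to hold. Section 6.2.1, which governs every 5.5.1 DLT, says to withhold and allows resumption one level lower. Arm 5 says to discontinue and takes the patient off protocol therapy.

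**Proteinuria.** Section 6.3 continues at a urine protein/creatinine ratio (UPC) of 1.9 or less. Section 5.2 requires 4.1.8.2 to be met again at each cycle start: urinalysis protein at most 30 mg/dL or dipstick at most 1+, unless 24-hour protein is under 1000 mg. Footnote 5 of 8.1 waives urinalysis when UPC is being followed.

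**The concern.** Two sites that follow the text literally can reach different decisions for the same child. Footnotes 14 and 15 of 8.1 address patients currently enrolled on Part B, so the text is in use. The DLT label also matters after Cycle 1: under 6.2.3 a DLT after two reductions means removal, and 11.2.1 makes a patient with a DLT at any time evaluable for adverse effects. If the hold rule and the DLT rule have different ranges, the toxicity description, which is a primary aim, depends on which passage was applied.

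**Working it through.** The plan gives no figure to reproduce. The check sets the passages side by side.

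**1. Range of the hold against range of the DLT** (treated, persisting more than 14 days)

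| Pressure | 5.5.1.2 | 6.4 |
|---|---|---|
| >0 to 10 mmHg above 95th percentile | not named | hold, reduced-dose restart |
| >10 to 25 mmHg above | DLT | hold, reduced-dose restart |
| >35 mmHg above baseline, but no more than 10 above the 95th percentile | not named | hold, reduced-dose restart |

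Example from Appendix VIII: boy aged 10, 50th height percentile, systolic limit 119; assumed baseline 90. A reading of 126 is 126 − 90 = 36 above baseline and 126 − 119 = 7 above the limit.

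**2. What the other DLT clauses leave open.** If antihypertensives start on Cycle 1 day d, the hold falls on about day d + 15. It lies in the 28-day cycle if d ≤ 13 and leaves 28 − (d + 15) + 1 = 14 − d hold days there.

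- d = 1 to 7: 13 to 7 days, so a hold of 7 days, which 5.5.1.5 needs, can fit.
- d = 8 to 13: 6 to 1 days, too few for 5.5.1.5 if only Cycle 1 days count.
- d ≥ 14: the hold begins in Cycle 2.

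For d = 8 to 13, 5.5.1.4 still captures a Grade 2 event: its 7 days apply to the toxicity, which has already lasted more than 14. What remains is an event below Grade 2 with a short hold. Its label turns on whether the reduction counts as required in Cycle 1 when the lower dose is first taken in Cycle 2.

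**3. Arm 1 against Arm 3.** A pressure can be at or below ULN and more than 35 above baseline whenever baseline < ULN − 35. Systolic limits at the 50th height percentile give:

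- boys ≥17: 136 − 35 = 101
- girls ≥17: 129 − 35 = 94
- boys aged 6: 114 − 35 = 79

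Example: boy ≥17, assumed baseline 98, reading 134. It is 136 − 134 = 2 below ULN (Arm 1: same dose) and 134 − 98 = 36 above baseline (Arm 3: treat, hold if persistent). The Arm 3 restart condition, pressure at or below ULN, is already met on the day the hold begins.

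**4. Grade 4 hypertension.** Footnote * groups it with pressure more than 25 mmHg above ULN, for which Arm 4 allows a reduced-dose restart. Section 6.2.1 allows resumption and states no exception. Arm 5 ends protocol therapy. No passage ranks the three.

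**5. Proteinuria.** Appendix VII equates UPC roughly with g/day, so 1000 mg corresponds to a UPC near 1.0. That holds only when creatinine excretion is about 1 g/day. In general, 24-hour protein (mg) = UPC × weight (kg) × creatinine excretion (mg/kg/day). Appendix VII gives 15 to 25 mg/kg/day for men and women; using it for children is an assumption. At 20 mg/kg/day:

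| Weight | Creatinine/day | UPC at 1000 mg | Protein at UPC 1.9 |
|---|---|---|---|
| 20 kg | 400 mg | 1000/400 = 2.5 | 760 mg |
| 50 kg | 1000 mg | 1.0 | 1900 mg |
| 70 kg | 1400 mg | 0.71 | 2660 mg |

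UPC 1.9 reaches 1000 mg at 1000/(1.9 × 20) = 26.3 kg (35.1 kg at 15 mg/kg/day, 21.1 kg at 25). Below that weight a 24-hour sample, if taken, meets 4.1.8.2 for every UPC that 6.3 allows. Above it, some patients continue under 6.3 but fail the exception.

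Without a 24-hour sample, 30 mg/dL is passed at UPC = 30/urine creatinine: 1.5, 1.0 and 0.3 at creatinine 20, 30 and 100 mg/dL (30 is the Appendix VII example; the others are assumed). A dipstick of 1+ or less would still satisfy 4.1.8.2. If only UPC is obtained, as footnote 5 permits, 4.1.8.2 has no UPC limit to compare it with.

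**6. Cross-references.** Reduced-dose restarts in Arms 3 and 4 point to 6.1.1 (hematological) and 6.2.2 (the removal rule).

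**The case against.** Much of this can be read in harmony. The DLT list is disjunctive, so capture by another clause is no error. Arm 3 restarts only at a lower dose, so the need for a reduction arguably arises when the hold starts. Holding can be the immediate action and Arm 5 the disposition. Section 5.2 can be an added cycle-start check beside the toxicity rule in 6.3. The missing flowchart may settle the order of Arms 1 and 3. Suspected DLTs go to the Study Chair: "Any suspected or confirmed dose-limiting toxicity should be reported immediately (within 24 hours) to the" that role. Section 14.4.2 adds a weekly central review.

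These readings are possible and narrow the problem, but the available text states none of them, and central reviewers work from the same passages. Dosing is continuous, so 6.3 and 5.2 meet at every cycle start.

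A reader might infer more than the documents support:

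- **That one reclassified patient could trip the closing rules in 11.1.** Enrollment was expected to need 3 to 6 more months after the January 2014 amendment, the adverse event list is dated October 2016 and pharmacology is marked complete. Accrual has probably ended, though no passage says so. Section 2.6 also reports a Cycle 1 DLT at 40 mg/m² in an expansion cohort without naming the part, so the starting count is uncertain.
- **That footnote * permits a restart after Grade 4 hypertension.** It gives no outcome after the hold.
- **That UPC 1.0 is where 6.3 and 5.2 part.** The boundary moves with weight.
- **That footnote 15, which thins Part B urinalysis, is a proteinuria defect.** It applies to most safety laboratory tests.

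**Conclusion.** The conflicts are real in the current text and should be fixed; their frequency is unknown.

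- **Hypertension.** The hold in 6.4 is wider than the range in 5.5.1.2. The DLT label is unclear mainly for events below Grade 2 with a hold under 7 days late in Cycle 1. The documents do not reproduce the CTCAE thresholds, so the number of such events cannot be judged. The overlap of Arms 1 and 3 holds unless the flowchart, not available here, sets the order.
- **Grade 4 hypertension.** Three passages give three instructions. Hold followed by removal is a possible reading that the text does not state.
- **Proteinuria.** Some patients may continue under 6.3 yet not start the next cycle under 5.2. No single UPC cut-off describes them.

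The case rests on decisions for individual patients and on consistent DLT labels. It does not claim that the dose recommendation or enrollment was affected.

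**What to change.** Amend the wording; the sponsor chooses each rule.

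- Align 5.5.1.2 with 6.4, or state whether each 6.4 hold or reduction arising in Cycle 1 is a DLT whatever the restart day.
- State which of Arm 1 and the Arm 3 baseline criterion governs when both apply.
- Give one outcome for Grade 4 hypertension across footnote *, Arm 5 and 6.2.1.
- Use one urine-protein measure and limit across 5.2 with 4.1.8.2, 6.3 and footnote 5 of 8.1, or state how the rules work together.
- Correct the references to 6.1.1 and 6.2.2 in Arms 3 and 4.

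The cost is a protocol amendment with no extra visits. A test is added only if the sponsor picks a urine measure that 8.1 does not now schedule.
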